### **5.3.5.5 Abnormal Vital Sign Values**

Not every vital sign abnormality qualifies as an AE. A vital sign result must be reported as an AE if it meets any of the following criteria:

- Is accompanied by clinical symptoms
- Results in a change in study treatment (e.g., dosage modification, treatment interruption, or treatment discontinuation)
- Results in a medical intervention or a change in concomitant therapy
- Is clinically significant in the Investigator or designee's judgment

It is the Investigator or designee's responsibility to review all vital sign findings. Medical and scientific judgment should be exercised in deciding whether an isolated vital sign abnormality should be classified as an AE.

If a clinically significant vital sign abnormality is a sign of a disease or syndrome (e.g., high blood pressure), only the diagnosis (i.e., hypertension) should be recorded on the Adverse Event eCRF and source form.

Observations of the same clinically significant vital sign abnormality from visit to visit should only be recorded once on the Adverse Event eCRF and source form (see Section 5.3.5.3 for details on recording persistent AEs).

### **5.3.5.6 Abnormal Liver Function Tests**

The finding of an elevated ALT or AST ( $>3 \times \text{ULN}$ ) in combination with either an elevated total bilirubin ( $>2 \times \text{ULN}$ ) or clinical jaundice in the absence of cholestasis or other causes of hyperbilirubinemia is considered to be an indicator of severe liver injury (as defined by Hy's Law). Therefore, Investigator or designees must report as an AE the occurrence of either of the following:

- Treatment-emergent ALT or AST  $>3 \times \text{ULN}$  in combination with total bilirubin  $>2 \times \text{ULN}$
- Treatment-emergent ALT or AST  $>3 \times \text{ULN}$  in combination with clinical jaundice

The most appropriate diagnosis or (if a diagnosis cannot be established) the abnormal laboratory values should be recorded on the Adverse Event eCRF and source form (see Section 5.3.5.1) and reported to the Sponsor immediately (i.e., no more than 24 hours after learning of the event), either as a SAE or an AESI (see Section 5.4.2).

### **5.3.5.7 Deaths**

All deaths that occur during the protocol-specified AE reporting period (see Section 5.3.1), regardless of relationship to study drug, must be recorded on the Adverse Event eCRF and source form and immediately reported to the Sponsor (see Section 5.4.2).

Death should be considered an outcome and not a distinct event. The event or condition that caused or contributed to the fatal outcome should be recorded as the single medical

concept on the Adverse Event eCRF and source form. Generally, only one such event should be reported. If the cause of death is unknown and cannot be ascertained at the time of reporting, "**unexplained death**" should be recorded on the Adverse Event eCRF and source form. If the cause of death later becomes available (e.g., after autopsy), "unexplained death" should be replaced by the established cause of death. The term "**sudden death**" should not be used unless combined with the presumed cause of death (e.g., "sudden cardiac death").

Deaths that occur after the AE reporting period should be reported as described in Section 5.6.

#### **5.3.5.8 Preexisting Medical Conditions**

A preexisting medical condition is one that is present at the screening visit for this study. Such conditions should be recorded on the General Medical History and Baseline Conditions eCRF.

A preexisting medical condition should be recorded as an AE only if the frequency, severity, or character of the condition worsens during the study. When recording such events on the Adverse Event eCRF and source form, it is important to convey the concept that the preexisting condition has changed by including applicable descriptors (e.g., "more frequent headaches").

#### **5.3.5.9 Hospitalization or Prolonged Hospitalization**

Any AE that results in hospitalization (i.e., inpatient admission to a hospital) or prolonged hospitalization should be documented and reported as an SAE (per the definition of SAE in Section 5.2.2), except as outlined below.

An event that leads to hospitalization under the following circumstances should not be reported as an AE or a SAE:

- Hospitalization for respite care
- Planned hospitalization required by the protocol
- Hospitalization for a preexisting condition, provided that all of the following criteria are met:
  - The hospitalization was planned prior to the study or was scheduled during the study when elective surgery became necessary because of the expected normal progression of the disease
  - The subject has not experienced an AE

An event that leads to hospitalization under the following circumstances is not considered to be a SAE, but should be reported as an AE instead:

- Hospitalization that was necessary because of subject requirement for outpatient care outside of normal outpatient clinic operating hours

#### **5.4 IMMEDIATE REPORTING REQUIREMENTS FROM INVESTIGATOR TO SPONSOR**

Certain events require immediate reporting to allow the Sponsor to take appropriate measures to address potential new risks in a clinical trial. The Investigator or designee must report such events to the Sponsor immediately; under no circumstances should reporting take place more than 24 hours after the Investigator or designee learns of the event. The following is a list of events that the Investigator or designee must report to the Sponsor within 24 hours after learning of the event, regardless of relationship to study drug:

- SAEs (defined in Section 5.2.2; see Section 5.4.2 for details on reporting requirements)
- [REDACTED] see Section 5.4.2 for details on reporting requirements)
- Pregnancies (see Section 5.4.3 for details on reporting requirements)

For SAEs and AESIs, the Investigator or designee must report new significant follow-up to the Sponsor immediately (i.e., no more than 24 hours after becoming aware of the information). New significant information includes the following:

- New signs or symptoms or a change in the diagnosis
- Significant new diagnostic test results
- Change in causality based on new information
- Change in the event's outcome, including recovery
- Additional narrative information on the clinical course of the event

Investigator or designees must also comply with local requirements for reporting SAEs to the local health authority and Institutional Review Board (IRB)/Ethics Committee (EC).

## **5.4.2 Reporting Requirements for Serious Adverse Events and Adverse Events of Special Interest**

### **5.4.2.1 Events that Occur prior to Study Drug Initiation**

After informed consent has been obtained but prior to initiation of study drug, only SAEs caused by a protocol-mandated intervention should be reported. The paper Clinical Trial Serious Adverse Event/AE of Special Interest Reporting Form provided to Investigator or designees should be completed and submitted to the Sponsor or its designee immediately (i.e., no more than 24 hours after learning of the event), either by faxing or by scanning and emailing the form using the fax number or email address provided to Investigator.

### **5.4.2.2 Events that Occur after Study Drug Initiation**

After initiation of study drug, SAEs and AEs of special interest will be reported until up to 14 days after the final dose of study drug. Investigator or designees should record all case details that can be gathered immediately (i.e., within 24 hours after learning of the event) on the paper Clinical Trial Serious Adverse Event/Adverse Event of Special Interest Reporting Form provided to investigators and submitting the report, either by faxing or by scanning and emailing the form using the fax number or email address provided to investigators.

Instructions for reporting SAEs that occur > 14 days after the last dose of study treatment are provided in Section [5.6](#).

## **5.4.3 Reporting Requirements for Pregnancies**

### **5.4.3.1 Pregnancies in Female Subjects**

Female subjects of childbearing potential will be instructed to immediately inform the Investigator or designee if they become pregnant during the study or within 90 days after the final dose of study drug. A paper Clinical Trial Pregnancy Reporting Form should be completed and submitted to the Sponsor or its designee immediately (i.e., no more than 24 hours after learning of the pregnancy), either by faxing or by scanning and emailing the form using the fax number or email address provided to the Investigator. Pregnancy should not be recorded on the Adverse Event eCRF and source form. The Investigator or designee should discontinue the study drug and counsel the subject, discussing the risks of the pregnancy and the possible effects on the fetus. Monitoring of the subject

should continue until conclusion of the pregnancy. Any SAE associated with the pregnancy (e.g., an event in the fetus, an event in the mother during or after the pregnancy, or a congenital anomaly/birth defect in the child) should be reported on the Adverse Event eCRF and source form. In addition, the Investigator or designee will submit a Clinical Trial Pregnancy Reporting Form when updated information on the course and outcome of the pregnancy becomes available.

#### **5.4.3.2 Pregnancies in Female Partners of Male Subjects**

Male subjects will be instructed through the Informed Consent Form to immediately inform the Investigator or designee if their partner becomes pregnant during the study or within 90 days after the final dose of study drug. A paper Clinical Trial Pregnancy Reporting Form should be completed and submitted to the Sponsor or its designee immediately (i.e., no more than 24 hours after learning of the pregnancy), either by faxing or by scanning and emailing the form using the fax number or email address provided to investigators. Attempts should be made to collect and report details of the course and outcome of any pregnancy in the partner of a male subject exposed to study drug. When permitted by the site, the pregnant partner would need to sign an Authorization for Use and Disclosure of Pregnancy Health Information to allow for follow-up on her pregnancy. If the authorization has been signed, the Investigator or designee should submit a Clinical Trial Pregnancy Reporting Form when updated information on the course and outcome of the pregnancy becomes available. An Investigator or designee who is contacted by the male subject or his pregnant partner may provide information on the risks of the pregnancy and the possible effects on the fetus, to support an informed decision in cooperation with the treating physician and/or obstetrician.

#### **5.4.3.3 Abortions**

A spontaneous abortion should be classified as an SAE (as the Sponsor considers abortions to be medically significant), recorded on the Adverse Event eCRF and source form, and reported to the Sponsor immediately (i.e., no more than 24 hours after learning of the event; see Section [5.4.2](#)).

If a therapeutic or elective abortion was performed because of an underlying maternal or embryofetal toxicity, the toxicity should be classified as an SAE, recorded on the Adverse Event eCRF, and reported to the Sponsor immediately (i.e., no more than 24 hours after learning of the event; see Section [5.4.2](#)). A therapeutic or elective abortion performed for reasons other than an underlying maternal or embryofetal toxicity is not considered an AE.

All abortions should be reported as pregnancy outcomes on the paper Clinical Trial Pregnancy Reporting Form.

#### **5.4.3.4 Congenital Anomalies/Birth Defects**

Any congenital anomaly/birth defect in a child born to a female subject exposed to study drug or the female partner of a male subject exposed to study drug should be classified as an SAE, recorded on the Adverse Event form, and reported to the Sponsor immediately (i.e., no more than 24 hours after learning of the event; see Section 5.4.2).

#### **5.4.4 Reporting Requirements for Cases of Accidental Overdose or Medication Error**

Accidental overdose and medication error (hereafter collectively referred to as "special situations"), are defined as follows:

- Accidental overdose: accidental administration of a drug in a quantity that is higher than the assigned dose
- Medication error: accidental deviation in the administration of a drug  
In some cases, a medication error may be intercepted prior to administration of the drug.

Special situations are not in themselves adverse events but may result in adverse events. Each AE associated with a special situation should be recorded separately on the Adverse Event eCRF. If the associated AE fulfills seriousness criteria, the event should be reported to the Sponsor immediately (i.e., no more than 24 hours after learning of the event; see Section 5.4.2). For balovaptan, adverse events associated with special situations should be recorded as described below for each situation:

- Accidental overdose: Enter the AE term. Check the "Accidental overdose" and "Medication error" boxes.
- Medication error that does not qualify as an overdose: Enter the AE term. Check the "Medication error" box.
- Medication error that qualifies as an overdose: Enter the AE term. Check the "Accidental overdose" and "Medication error" boxes.

In addition, all special situations associated with balovaptan, regardless of whether they result in an AE, should be recorded on the Adverse Event eCRF as described below:

- Accidental overdose: Enter the drug name and "accidental overdose" as the event term. Check the "Accidental overdose" and "Medication error" boxes.
- Medication error that does not qualify as an overdose: Enter the name of the drug administered and a description of the error (e.g., wrong dose administered, wrong dosing schedule, incorrect route of administration, wrong drug, expired drug administered) as the event term. Check the "Medication error" box.
- Medication error that qualifies as an overdose: Enter the drug name and "accidental overdose" as the event term. Check the "Accidental overdose" and "Medication error" boxes. Enter a description of the error in the additional case details.

- Intercepted medication error: Enter the drug name and "intercepted medication error" as the event term. Check the "Medication error" box. Enter a description of the error in the additional case details.

As an example, an accidental overdose that resulted in a headache would require 2 entries on the Adverse Event eCRF, one entry to report the accidental overdose and one entry to report the headache. The "Accidental overdose" and "Medication error" boxes would need to be checked for both entries.

## **5.5 FOLLOW-UP OF SUBJECTS AFTER ADVERSE EVENTS**

### **5.5.1 Investigator Follow-Up**

The Investigator or designee should follow each AE until the event has resolved to baseline grade or better, the event is assessed as stable by the Investigator or designee, the subject is lost to follow-up, or the subject withdraws consent. Every effort should be made to follow all SAEs considered to be related to study drug or trial-related procedures until a final outcome can be reported.

During the study period, resolution of adverse events (with dates) should be documented on the Adverse Event eCRF and source form and in the subject's medical record to facilitate source data verification.

All pregnancies reported during the study should be followed until pregnancy outcome.

### **5.5.2 Sponsor Follow-Up**

For SAEs, and pregnancies, the Sponsor or a designee may follow up by telephone, fax, email, and/or a monitoring visit to obtain additional case details and outcome information (e.g., from hospital discharge summaries, consultant reports, autopsy reports) in order to perform an independent medical assessment of the reported case.

## **5.6 ADVERSE EVENTS THAT OCCUR AFTER THE ADVERSE EVENT REPORTING PERIOD**

The Sponsor should be notified if the Investigator or designee becomes aware of any SAE that occurs after the end of the AE reporting period (defined as 14 days after the final dose of study drug), if the event is believed to be related to prior study drug treatment. These events should be reported through use of the Adverse Event eCRF and source form. The Investigator or designee should report these events directly to the Sponsor or its designee, either by faxing or by scanning and emailing the paper Clinical Trial Serious Adverse Event/Adverse Event of Special Interest Reporting Form using the fax number or email address provided to investigators.

## **5.7 EXPEDITED REPORTING TO HEALTH AUTHORITIES, INVESTIGATORS, INSTITUTIONAL REVIEW BOARDS, AND ETHICS COMMITTEES**

The Sponsor will promptly evaluate all SAEs and AESI against cumulative product experience to identify and expeditiously communicate possible new safety findings to Investigator (or designee), IRBs, ECs, and applicable health authorities based on applicable legislation.

Independent from the causality assessment, the following SAEs and non-SAEs of special interest will be reported to the FDA on an expedited basis: death, arrhythmia, syncope, dyspnea, palpitations, and chest pain.

To determine reporting requirements for single AE cases, the Sponsor will assess the expectedness of these events through use of the reference safety information in the documents listed below:

Drug	Document
Balovaptan	RO5285119 V1a Receptor Antagonist (Balovaptan) Investigator's Brochure
Esomeprazole	Esomeprazole US Package Insert

The Sponsor will compare the severity of each event and the cumulative event frequency reported for the study with the severity and frequency reported in the applicable reference document.

Reporting requirements will also be based on the Investigator or designee's assessment of causality and seriousness, with allowance for upgrading by the Sponsor as needed.

An aggregate report of any clinically relevant imbalances that do not favor the test product will be submitted to health authorities.

## **6. STATISTICAL CONSIDERATIONS AND ANALYSIS PLAN**

A statistical analysis plan will be generated and will be finalized prior to database lock.

### **6.1 DETERMINATION OF SAMPLE SIZE**

Sixteen subjects will be enrolled with the target of at least 12 evaluable subjects available for the final PK analysis. Considering the observed residual CV% for AUC0-inf from Study WP40038 of approximately 14%, with 12 subjects the 90% CI would be obtained by dividing/multiplying the ratio estimate by a factor of 1.11.

### **6.2 SUMMARIES OF CONDUCT OF STUDY**

The number of subjects who enroll, discontinue, or complete the study will be summarized. Reasons for premature study withdrawal will be listed and summarized.

Enrollment and major protocol deviations will be listed and evaluated for their potential effects on the interpretation of study results.

### **6.3 SUMMARIES OF DEMOGRAPHIC AND BASELINE CHARACTERISTICS**

Demographic and baseline characteristics will be summarized using means, standard deviations, medians, and ranges for continuous variables and proportions for categorical variables, as appropriate. Summaries will be presented overall and by treatment sequence.

### **6.4 EFFICACY ANALYSES**

Not Applicable

### **6.5 SAFETY ANALYSES**

The Safety population will include all subjects who are randomized and receive at least one dose of the study medication (either balovaptan or esomeprazole), whether prematurely withdrawn from the study or not.

Safety will be assessed through summaries of exposure to study treatment, adverse events, changes in laboratory test results, and changes in vital signs and ECGs.

Study treatment exposure (such as treatment, duration [as applicable], and total dose received) will be summarized with descriptive statistics.

All verbatim AE terms will be mapped to Medical Dictionary for Regulatory Activities thesaurus terms, and AE severity will be graded according to [Table 3](#). All AEs, SAEs, AEs leading to death, AESIs, and AEs leading to study treatment discontinuation that occur on or after the first dose of study treatment (i.e., treatment-emergent adverse events) will be summarized by mapped term, appropriate thesaurus level, and severity grade. For events of varying severity, the highest grade will be used in the summaries. Deaths and cause of death will be summarized.

Relevant laboratory, vital sign (pulse rate, respiratory rate, blood pressure, and temperature), and ECG data will be displayed by time, with grades identified where appropriate. Additionally, a shift table of selected laboratory tests will be used to summarize the baseline and maximum postbaseline severity grade. Changes in vital signs and ECGs will be summarized.

### **6.6 PHARMACOKINETICS ANALYSES**

The PK population will include all subjects who receive at least 1 dose of balovaptan and have sufficient evaluable concentrations to determine the overall exposure to balovaptan.

Subjects will be excluded from the PK analysis population if they significantly violate the inclusion or exclusion criteria, deviate significantly from the protocol, or if data are

unavailable or incomplete. Excluded cases will be documented together with the reason for exclusion. All decisions on exclusions from the analysis will be made prior to database lock.

The following balovaptan, metabolites M2 (as appropriate) and M3, and esomeprazole PK parameters will be estimated:

- $C_{max}$ : maximum plasma concentration
- $AUC_{(0-inf)}$ : area under the concentration-time curve from time extrapolated to infinity
- $AUC_{(0-24h)}$ : area under the concentration-time curve from time 0 to 24 hours
- $AUC_{last}$ : area under the concentration-time curve from time 0 to the time of the last quantifiable concentration
- $T_{max}$ : time to reach  $C_{max}$  in plasma
- $C_{last}$ : last quantifiable concentration
- $T_{last}$ : time to the last quantifiable concentration
- $T_{lag}$ : time between dosing and time of first balovaptan plasma concentration.
- $Cl/F$ : apparent clearance
- $Vd/F$ : apparent volume of distribution
- $T_{1/2}$ : terminal elimination phase half-life

Individual and mean concentration versus time data will be plotted on linear and semilogarithmic scales. Plasma concentrations and derived plasma PK parameters will be listed for balovaptan and its metabolites. Summary statistics of PK parameters, including means, geometric means, medians, ranges, SD, CV% will be presented for each treatment. Analysis of variance models will be applied to the logarithmically transformed PK parameters of balovaptan  $AUC_{0-inf}$  and  $C_{max}$ , to investigate 1) the relative bioavailability of balovaptan 20-mg dispersible tablets administered following a high-fat, high-calorie meal vs in the fasted state, and 2) the relative bioavailability of balovaptan 20-mg dispersible tablets administered in the fasted state either alone or in combination with esomeprazole.

The effect of food on the PK of balovaptan will be assessed using the ratio and 90% CIs of the geometric least squares (LS) means of the plasma PK parameters  $C_{max}$  and  $AUC_{0-inf}$  for balovaptan. A linear mixed model with fixed effects for treatment, period, sequence, and a random effect for subject nested in sequence will be used on the natural log-transformed parameters. Point estimates on the natural log scale will be exponentiated to obtain point estimates on the original scale of measurement. Geometric LS means will be provided for each treatment. Food had no relevant effect on the overall exposure of the capsule formulation of balovaptan but  $T_{max}$  was shifted from 1 hour after dosing under fasted conditions to approximately 3 hours in fed conditions.

The effect of esomeprazole on the PK of balovaptan will be assessed using the ratio and 90% CIs of the geometric LS means of the plasma PK parameters:  $C_{max}$  and  $AUC_{0-inf}$  for balovaptan. A linear mixed model with a fixed effect for treatment and a random effect for subject will be used on the natural log-transformed parameters. Point estimates on the natural log scale will be exponentiated to obtain point estimates on the original scale of measurement. LS geometric means will be provided for each treatment.

In all comparisons, balovaptan under fasted conditions will be used as the reference. No adjustments will be made for multiplicity.

PK parameters will be estimated using standard noncompartmental methods.

Additional PK analyses maybe be conducted as appropriate for balovaptan, M2, and M3.

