### Objectives and Endpoints

This study will investigate the effect of food and the effect of esomeprazole on the pharmacokinetics (PK) of a single dose of balovaptan in healthy volunteers.

Objective	Endpoints
Primary Objectives	

 
• To investigate the effect of esomeprazole on the PK of balovaptan following a single oral dose of balovaptan in the fasted state
 
• To investigate the effect of a high-fat meal compared to the fasted state on the PK of balovaptan following a single oral dose of balovaptan
 
	
 
• Plasma concentrations of balovaptan
 
• Derived plasma PK parameters for balovaptan
 

Secondary Objectives	

 
• To investigate the effect of esomeprazole on the PK of M2 (as appropriate) and M3 following a single oral dose of balovaptan in the fasted state
 
• To investigate the effect of a high-fat meal compared to the fasted state on the PK of M2 (as appropriate) and M3 following a single oral dose of balovaptan
 
• To measure the PK of esomeprazole following 5 once daily doses of esomeprazole
 
	
 
• Plasma concentrations of M2 and M3
 
• Derived plasma PK parameters for M2 and M3
   
• Plasma concentrations of esomeprazole
 
• Derived plasma PK parameters for esomeprazole
 

 
To investigate the safety and tolerability of a single 20 mg oral dose of balovaptan alone or in combination with esomeprazole in healthy subjects
 
	
 
Incidence and severity of AEs, incidence of SAEs, non-serious AESIs, and AEs leading to treatment withdrawal
 
Results of vital signs, 12-lead ECGs, physical examinations, and clinical laboratory tests
 

Exploratory Objectives	

 
To explore the effect of genetic variations in genes associated with drug ADME, and transport on the PK and/or safety profile of balovaptan.
 
	
 
Genotyping data for study subjects. Data will be reported separately if analysis is conducted
 

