**Table 1 Objectives and Corresponding Endpoints**

Objective	Endpoints
Primary Objectives	

 
To investigate the effect of esomeprazole on the PK of balovaptan following a single oral dose of balovaptan in the fasted state
 
To investigate the effect of a high-fat meal compared to the fasted state on the PK of balovaptan following a single oral dose of balovaptan
 
	
 
Plasma concentrations of balovaptan
 
Derived plasma PK parameters for balovaptan
 

Secondary Objectives	

 
To investigate the effect of esomeprazole on the PK of M2 (as appropriate) and M3 following a single oral dose of balovaptan in the fasted state
 
To investigate the effect of a high-fat meal compared to the fasted state on the PK of M2 (as appropriate) and M3 following a single oral dose of balovaptan
 
To measure the PK of esomeprazole following 5 once daily dosing of esomeprazole
 
	
 
Plasma concentrations of M2 and M3
 
Derived plasma PK parameters for M2 and M3
 
Plasma concentrations of esomeprazole
 
Derived plasma PK parameters for esomeprazole
 

Objective	Endpoints

 
To investigate the safety and tolerability of a single 20 mg oral dose of balovaptan alone or in combination with esomeprazole in healthy subjects
 
	
 
Incidence and severity of AEs, incidence of SAEs, nonserious AESIs, and AEs leading to treatment withdrawal
 
Results of vital signs, 12-lead ECGs, physical examinations, and clinical laboratory tests
 

Exploratory Objectives	

 
To explore the effect of genetic variations in genes associated with drug ADME and transport on the PK and/or safety profile of balovaptan.
 
	
 
Genotyping data for study subjects. Data will be reported separately if analysis is conducted
 

ADME=absorption, distribution, metabolism, excretion; AE=adverse event; AESI=adverse event of special interest; ECG=electrocardiogram; PK=pharmacokinetics; SAE=serious adverse event;

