## Appendix 1: Schedule of Activities

	Scr	Period 1								Period 2								Period 3								F/U
	D -28 to -2	D -1	D 1	D 2	D 3 & 4	D 5	D 7	D 9	w/o	D -1	D1	D 2	D 3 & 4	D 5	D 7	D 9	D10 to D12	D 13 a	D -1 a	D 1	D 2	D 3 & 4	D 5	D 7	D 9	D16 ±2 or ET
Biochemistry	X	X				X				X				X		X			X				X			X
Urinalysis	X	X																								X
Coagulation	X	X																								X
Urine drug and alcohol screen l	X	X								X					X											
Serology	X																									
Pregnancy test m	X	X								X					X											X
FSH n	X																									
Genotyping sample		X																								
Adverse event monitoring	X	X	X	X	X	X	X	X		X	X	X	X	X	X	X	X	X	X	X	X	X	X	X	X	X

ET=early termination; F/U= follow-up; FSH=follicle-stimulating hormone; w/o=washout

- Day 13 of Period 2 is Day -1 of Period 3.
- Balovaptan will be administered following a high-fat, high-calorie meal (Treatment A) or after a ≥ 10 h fast (Treatments B and C). Subjects should fast for 4 hours after balovaptan administration and refrain from drinking for 1 hour prior to and 1 hour post dose.
- Esomeprazole will be administered 1 hour prior to balovaptan.
- Standardized meals will be provided at approximately 4 and 8 hours post-balovaptan dosing in each treatment period
- Samples at predose, and at 0.25, 0.5, 1, 1.5, 2, 2.5, 3, 3.5, 4, 5, 6, 8, 12, 16, 24, 36, 48, 72, 96, 144, and 192 hours post dose
- Samples at predose, 0.25, 0.5, 1, 1.5, 2, 3, 4, 6, 8 hours post dose of esomeprazole
- Height, weight, and BMI calculation at screening; only weight at all follow-up.
- Safety ECG will be performed in triplicate at Screening and on Day -1 of each period; at all other time points single ECGs will be performed.
- Body temperature and respiratory rate will be measured at Screening and Day -1 of each period only.
- Orthostatic challenge testing will be performed at screening.
- On Day 1, vital signs measurements will be performed at 1 hour post dose.
- Drugs of abuse (amphetamines [including ecstasy], barbiturates, benzodiazepines, cannabinoids, cocaine, cotinine, opiates, methamphetamines, and methadone).
- Serum pregnancy test performed on all female subjects at Screening and Day -1 of each treatment period (Day 13 of Period 2 is Day -1 of Period 3) and at follow-up.
- In postmenopausal women to confirm menopause

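### Does applying one PK parameter list to balovaptan, M2, M3 and esomeprazole in Section 6.6 make the secondary PK results unsound?

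*Combined protocol and SAP*

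**What the plan says.** Section 6.6 (Pharmacokinetics Analyses) states: "The following balovaptan, metabolites M2 (as appropriate) and M3, and esomeprazole PK parameters will be estimated". Eleven parameters follow, with no restriction by analyte; the only qualifier applies to M2. Three entries matter here:

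- AUC(0-24h), defined as "area under the concentration-time curve from time 0 to 24 hours".
- Cl/F, defined as "apparent clearance", and the matching volume Vd/F.
- Tlag, defined as "time between dosing and time of first balovaptan plasma concentration", which shows that the list was drafted for the parent drug.

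AUClast, Clast and Tlast are also on the list.

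The esomeprazole sampling footnote in Appendix 1 reads "Samples at predose, 0.25, 0.5, 1, 1.5, 2, 3, 4, 6, 8 hours post dose of esomeprazole", on Day 1 of Period 3. Balovaptan is sampled to 192 h, including at 24 h. The only statement of method is "PK parameters will be estimated using standard noncompartmental methods".

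These quantities support secondary objectives: the synopsis lists "Derived plasma PK parameters for esomeprazole" and Table 1 lists "Derived plasma PK parameters for M2 and M3". The formal models in Section 6.6 use balovaptan Cmax and AUC0-inf only. Section 6 says that a separate SAP will be finalized before database lock; it is not part of the text reviewed.

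**The concern.** Read literally, the list asks for things the data do not directly give.

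For esomeprazole, 24 − 8 = 16 of the 24 hours are unsampled. An AUC(0-24h) can still be produced, but its value depends on how the gap is filled, and the protocol names no rule, no label and no limit on the extrapolated share. Two analysts could report different numbers for the same secondary endpoint.

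For M2 and M3, dividing the balovaptan dose by the metabolite AUC does not give the metabolite's clearance over F. It gives that quantity divided by the fraction of balovaptan converted. A table headed Cl/F would be open to misreading, possibly by a large factor.

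At stake would be absolute values in secondary summary tables that are either rule-dependent or mislabelled.

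**Working it through.** **The plan's own figure.** Section 6.1 gives a residual CV of 14%, 12 subjects and a 90% CI factor of 1.11 for balovaptan AUC0-inf.

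- s = √ln(1 + 0.14²) = 0.1393
- t(0.95; 10 df) = 1.812
- factor = exp(1.812 × 0.1393 × √(2/12)) = 1.109, which rounds to 1.11

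It reproduces, and no esomeprazole or metabolite quantity enters it.

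**Esomeprazole: how much area lies after 8 h.** The protocol gives no esomeprazole half-life, absorption rate or lag, so all three are assumed. With k = ln 2 / half-life:

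- Mono-exponential share after 8 h = (e^(−8k) − e^(−24k)) / (1 − e^(−24k)).
- One-compartment oral model: C(t) ∝ [ka/(ka − k)] × [e^(−k(t − lag)) − e^(−ka(t − lag))], with ka from 1 to 3 per h and lag from 0 to 1 h. The share is the area from 8 to 24 h over the area from 0 to 24 h.

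| Assumed half-life | Mono-exponential | Oral model, range |
|---|---|---|
| 1 h | 0.4% | 0.5–2.3% |
| 2 h | 6.2% | 7.0–13.4% |
| 3 h | 15.4% | 16.7–25.3% |
| 4 h | 23.8% | 25.3–34.5% |

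**Esomeprazole: how much the rule matters.** The profile is the fifth daily dose with ka 1.5 per h and lag 0.5 h. Each entry is the result divided by the true AUC(0-24h).

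| Rule | 1 h | 2 h | 3 h | 4 h |
|---|---|---|---|---|
| Terminal slope from 4, 6 and 8 h | 1.000 | 1.001 | 1.002 | 1.003 |
| Log-linear from 8 h to the predose value placed at 24 h | 1.000 | 1.000 | 1.000 | 1.000 |
| Linear trapezoid from 8 h to the predose value placed at 24 h | 1.047 | 1.173 | 1.193 | 1.168 |
| Stop at 8 h | 0.990 | 0.904 | 0.795 | 0.706 |

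The ratio of the highest to the lowest rule is 1.06, 1.30, 1.50 and 1.65. That spread comes entirely from the last two rows. Stopping at 8 h is not an AUC(0-24h); it is AUClast, which the list already requests under its own name. A straight line across a 16 h gap is one possible convention, and nothing in the protocol points to it. The two rules that respect exponential decline agree with each other and with the truth. These curves are noise-free, so real data would scatter more, but the alleged error was derived from the same noise-free curves.

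**M2 and M3.** With metabolite clearance CLm:

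- AUCm = F × fm × Dose / CLm, so Dose / AUCm = CLm / (F × fm).
- The volume carries the same factor 1/fm.
- At assumed fm of 0.5, 0.3 and 0.1 the factor is 2.0, 3.3 and 10.

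For two treatments at the same 20 mg dose, the ratio of Dose/AUCm is simply the inverse of the AUCm ratio. If fm is constant across treatments it cancels, and the comparison reads correctly as a comparison of CLm/F. Metabolite Cmax, AUC and half-life do not involve fm in their calculation.

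**The case for a change.** The strongest case for a change is that it costs only words. The list is unconditional for M3 and esomeprazole, the Tlag wording shows it was not adapted to the other analytes, and Section 6.6 promises summary statistics by treatment, so ambiguous absolute values could reach the report. Noncompartmental software offers several conventions and the protocol picks none. At an assumed half-life of 2 h, two mechanical choices already differ by 1.173 / 0.904 = 1.30.

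The gap in wording stands, and so does the algebra for metabolites. Three things weaken the rest:

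- The size rests on half-lives and conversion fractions that the documents do not give, and on two rules that an analyst working by standard noncompartmental methods has no reason to choose for this quantity.
- A reader can already see how much of the area was observed, because AUClast and Tlast are reported beside AUC(0-24h). When the 8 h sample is quantifiable, AUClast is AUC(0-8h).
- It cannot be said that the plan lacks a conversion fraction: the metabolism text in Sections 1.2 and 1.2.1.1 is partly blacked out.

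Some remedies would also do little good. A 20% cap on extrapolation has no source in the documents and, on the figures above, would reject every assumed 4 h profile. Dropping AUC(0-24h) would remove the dosing-interval exposure of a drug given once daily.

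**Conclusion.** The observation is accurate, but it is missing detail that analysts fill sensibly, and no change to the plan follows. Followed as written, Section 6.6 still yields sound results. Esomeprazole AUC(0-24h) would include an extrapolated part of roughly 0.5% to 13% at assumed half-lives of 1 to 2 h, rising to about 25–35% at 4 h, and ordinary terminal-slope extrapolation would bring it within 0.3% of the truth in idealised profiles. Metabolite Cl/F and Vd/F would be CLm/(F × fm) and Vm/(F × fm), where Vm is the metabolite volume; that is a matter of labelling.

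No balovaptan comparison, design figure or study conclusion depends on either point, and between-treatment metabolite comparisons are unaffected if fm is constant. Naming the extrapolation rule and relabelling the metabolite terms is routine tidying for the SAP. The conclusion assumes that the analyst treats the 8 to 24 h segment as exponential decline, and that the esomeprazole half-life is short enough for 4, 6 and 8 h to define a terminal slope.
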